14.0 DATA HANDLING CONVENTIONS

14.1 VISIT TIME WINDOWS

The analyses will be based on nominal visits from CRFs.

14.2 DERIVED VARIABLES

14.3 REPEATED OR UNSCHEDULED ASSESSMENTS OF SAFETY PARAMETERS

If a patient has repeated assessments before the start of the first treatment, the results from the final non-missing assessment made prior to the start of the study treatment will be used as baseline. If end-of-study assessments are repeated or if unscheduled visits occur, the last non-missing postbaseline assessment will be used as the end-of-study assessment for generating summary statistics. However, all postbaseline assessments will be used for PCS value determinations, and all assessments will be presented in the data listings.

14.4 MISSING DATE OF THE LAST DOSE OF STUDY TREATMENT

When the date of the last dose of study treatment is missing for a patient in the Safety Population, all efforts should be made to obtain the date from the Investigator. If after all efforts are made it is still missing, the last available dosing record date will be used as the last dose date.

14.5 MISSING SEVERITY ASSESSMENT FOR ADVERSE EVENTS

If severity is missing for an AE that started before the date of the first dose of study treatment, an intensity of mild will be assigned. If severity is missing for an AE that started on or after the date of the first dose of study treatment, an intensity of severe will be assigned. The imputed values for severity assessment will be used for the incidence summary; the values will be shown as missing in the data listings.

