10.1 ADVERSE EVENTS

Adverse events will be coded by system organ class and preferred term using the *Medical Dictionary for Regulatory Activities*, version 20.1 or newer.

An AE will be considered a treatment-emergent adverse event (TEAE) if it was present one or after the first application of study treatment or was present before the date of the first application of study treatment and increased in severity or became serious on or after the first application of study treatment.

An AE will be considered a treatment-emergent serious AEs (TESAE) if it is a TEAE that additionally meets any SAE criteria.

The number and percentage of patients reporting TEAEs and treatment-related TEAEs in each treatment group will be tabulated by system organ class and preferred term, separately. If more than 1 AE is coded to the same preferred term for the same patient, the patient will be counted only once for that preferred term using the greatest severity.

A summary table will be provided for subjects with TEAE, TESAE, death and subjects with TEAEs leading to discontinuation if 5 or more participants reported such events. A subject listing of all AEs will be presented.

11.0 **INTERIM ANALYSIS**

No interim analysis is planned for this study.

12.0 **DETERMINATION OF SAMPLE SIZE**

As this is a proof of concept study, no formal calculation of sample size was conducted. Approximately 70 participants will be enrolled to achieve approximately 60 completed.

13.0 **STATISTICAL SOFTWARE**

Statistical analyses will be performed using version [REDACTED]
[REDACTED]

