14.6 MISSING CAUSAL RELATIONSHIP TO STUDY TREATMENT FOR ADVERSE EVENTS

[If the 3-point scale for relationship to study treatment is used (ie, “Not related,” “Possibly related,” and “Related”), the relevant text below may need to be modified accordingly. For example, “causal relationship” would become “relationship” and “yes” would become “*related*.”]

If the causal relationship to the study treatment is missing for an AE that started on or after the date of the first dose of study treatment, a causality of yes will be assigned. The imputed values for causal relationship to study treatment will be used for the incidence summary; the values will be shown as missing in the data listings.

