14.7 MISSING DATE INFORMATION FOR ADVERSE EVENTS

The following imputation rules only apply to cases in which the start date for AEs is incomplete (ie, partly missing).

Missing month and day

- If the year of the incomplete start date is the same as the year of the first dose of study treatment, the month and day of the first dose of study treatment will be assigned to the missing fields
- If the year of the incomplete start date is before the year of the first dose of study treatment, *December 31* will be assigned to the missing fields
- If the year of the incomplete start date is after the year of the first dose of study treatment, *January 1* will be assigned to the missing fields

Missing month only

- If only the month is missing, the day will be treated as missing and both the month and the day will be replaced according to the above procedure

Missing day only

- If the month and year of the incomplete start date are the same as the month and year of the first dose of study treatment, the day of the first dose of study treatment will be assigned to the missing day
- If either the year of the incomplete start date is before the year of the date of the first dose of study treatment or if both years are the same but the month of the incomplete start date is before the month of the date of the first dose of study treatment, the last day of the month will be assigned to the missing day
- If either the year of the incomplete start date is after the year of the date of the first dose of study treatment or if both years are the same but the month of the incomplete start date is after the month of the date of the first dose of study treatment, the first day of the month will be assigned to the missing day

If the stop date is complete and the imputed start date as above is after the stop date, the start date will be imputed by the stop date.

If the start date is completely missing and the stop date is complete, the following algorithm will be used to impute the start date:

- If the stop date is after the date of the first dose of study treatment, the date of the first dose of study treatment will be assigned to the missing start date
- If the stop date is before the date of the first dose of study treatment, the stop date will be assigned to the missing start date.

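### Missing AE severity and causality are imputed by start date, so a pre-dose AE that becomes treatment-emergent can miss the SAP's conservative defaults

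*SAP*

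**What the plan says.** SAP 10.1 defines a TEAE in two limbs. The first covers events present once treatment has been applied. The second covers an AE "present before the date of the first application of study treatment and increased in severity or became serious on or after" first application. TEAEs and treatment-related TEAEs are each tabulated by system organ class and preferred term. A patient with several AEs under one preferred term counts once, at the greatest severity.

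The rules for missing fields do not mention TEAE status:

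- **Severity (SAP 14.5).** "If severity is missing for an AE that started before the date of the first dose of study treatment, an intensity of mild" is assigned; for one that "started on or after the date of the first dose of study treatment, an intensity of severe will be assigned".
- **Causality (SAP 14.6).** For an AE that "started on or after the date of the first dose of study treatment, a causality of yes will be assigned". There is no rule for earlier onsets.
- **Dates (SAP 14.7).** "If the start date is completely missing and the stop date is complete, the following algorithm will be used", with one branch for a stop date after first dose and one for a stop date before it. A stop on the day of first dose is not covered, and neither is an ongoing AE with no start date.

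Imputed severity and causality feed the incidence summaries, while the listings show the fields as missing. Protocol 9.0 starts AE capture at study entry. Screening precedes Day 0, so an AE with onset before first application can be on the form.

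**The concern.** For an AE that begins on treatment, the SAP takes the cautious course: missing severity becomes severe and missing causality becomes yes. A pre-dose AE that qualifies as a TEAE under the second limb of 10.1 is a treatment-emergent event like any other, yet it does not get the same protection. If its causality is missing, nothing places it in the treatment-related TEAE table. If it became serious and its severity is missing, it is labelled mild. Both outcomes run against the evident intent of the defaults, and safety is part of the study's stated primary objective.

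The gaps in 14.7 add to this. Sections 14.5 and 14.6 both need a start date, so an AE left without one receives neither default.

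**Working it through.** The documents give no figure to reproduce, because this is a data-handling rule and no formal sample-size calculation was done. The check is therefore a comparison of rules, followed by a bound on size.

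**Step 1. Apply SAP 14.5 and 14.6 to each type of AE, then apply defaults that follow TEAE status.**

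| AE type | SAP result (severity / causality) | Result by TEAE status |
|---|---|---|
| Pre-dose onset, not a TEAE, both missing | mild / none | mild / none |
| Pre-dose onset, became serious on treatment, both missing | mild / none | severe / yes |
| Pre-dose onset, worsened with later severity recorded, causality missing | recorded severity / none | recorded severity / yes |
| Worsening entered as a new on-treatment record, both missing | severe / yes | severe / yes |
| On-treatment onset, both missing | severe / yes | severe / yes |

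Only the second and third rows differ. Causality is affected in both, severity only in the second.

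**Step 2. Trace the effect to the planned outputs.** The treatment-related TEAE table depends on causality, so a missing value with no default can remove an event from it. The mild label does not remove a patient from the TEAE counts. In the visible text, severity enters only through the count-once rule. An event that became serious also remains a treatment-emergent serious AE whatever its severity label. Causality is therefore the main route to understatement.

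**Step 3. Size per event.** About 70 participants randomized 1:1 gives 70/2 = 35 per arm; about 60 completers gives 60/2 = 30.

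- 1/35 = 2.9 percentage points per affected patient.
- 1/30 = 3.3 percentage points per affected patient.

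**Step 4. How many events?** The documents give neither rate needed, so both are assumptions. Let p be the share of patients with a pre-dose AE that becomes a TEAE (1% to 10%), and m the share of those with causality missing (1% to 20%). Expected patients affected per arm = n × p × m. The probability of at least one = 1 − (1 − p × m)^n.

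| n per arm | p | m | Expected patients | P(at least one) |
|---|---|---|---|---|
| 35 | 1% | 1% | 0.004 | 0.4% |
| 35 | 5% | 5% | 0.09 | 8% |
| 35 | 10% | 20% | 0.70 | 51% |
| 30 | 1% | 1% | 0.003 | 0.3% |
| 30 | 10% | 20% | 0.60 | 45% |

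Even at the high end, fewer than one patient per arm is expected.

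**The case against.** The strongest reply is that the rules seldom act. They apply only to missing fields. The protocol has the investigator evaluate seriousness and relatedness (9.2) and intensity (9.5), requires written reporting of SAEs within 24 hours (9.5), and makes the investigator responsible for complete CRFs (13.6). A serious AE with no severity should be rare. This stands, and it limits the size of the point.

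Second, Protocol 9.1 treats a clinically relevant deterioration in a clinical finding as an AE to be recorded. If a worsening is entered as its own record, its onset is on treatment and it already gets severe and yes. That would close the severity and causality gaps, but neither document says that worsening or new seriousness must be a separate record, and the second limb of 10.1 presupposes that it may not be.

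A reader might also infer more than the documents support:

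- **That pre-dose AEs which worsen generally default to mild.** Showing a worsening normally needs a recorded post-dose severity, and then 14.5 imputes nothing. If only the pre-dose grade is missing, setting it to mild makes a later higher grade more likely to count as an increase, which is conservative.
- **That the error always understates harm, or favours one device.** Section 14.7 moves partial start dates in the month or year of first dose to the first-dose date, which brings them under the severe and yes rules. The rules apply to both arms, and no between-arm bias is shown.
- **That severity tables would be distorted.** No table by severity is described in the visible text; table specifications are in a separate document.
- **That an AE with no start date cannot be classed as a TEAE.** The first limb of 10.1 turns on presence once treatment has been applied, so an ongoing AE can meet it. What fails is the application of 14.5 and 14.6.
- **That the share of follow-up before first dose measures the problem.** Calendar time says nothing about how often fields are missing.

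**Conclusion.** The point holds as a narrow inconsistency. The TEAE definition in 10.1 is wider than the start-date condition in 14.5 and 14.6. A pre-dose-onset TEAE with missing causality can therefore drop out of the treatment-related table, and a pre-dose AE that became serious with missing severity is labelled mild. Both can understate harm; the documents do not show that they will.

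The effect per event is about 2.9 percentage points in an arm of 35. Under the assumed mid-range rates (5% and 5%) the chance of any affected patient in an arm is about 8%. This is a minor correction, worth making because the rules contradict the SAP's own cautious approach and cost little to align. The conclusion assumes that worsening or new seriousness is not routinely entered as a new AE record.

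**What to change.** - **SAP 14.6:** apply the related default to every TEAE with missing causality, including those with pre-dose onset. TEAE status does not depend on causality, so this is not circular.
- **SAP 14.5:** assign severe when severity is missing for an AE that began on or after first application, or that began earlier and became serious afterwards. Keep mild for other pre-dose AEs. Using seriousness avoids the circularity of deriving severity from a status that itself depends on severity. It also avoids calling every ongoing background condition severe, which would go beyond 10.1.
- **Alternative to both:** state that worsening or seriousness arising after first application is entered as a new AE record. The existing severe and yes defaults then apply.
- **SAP 14.7:** where the start date is completely missing, extend the branch for a stop after first dose to a stop on or after it, and assign the first-dose date when the AE is ongoing.

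While 14.6 is open, remove its bracketed template text and map its yes category to the scale in Protocol 9.3. Say also how a recorded entry of not applicable is handled if that AE later becomes a TEAE.

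The cost is a few SAP sentences and a small programming change. The downside is that an occasional event is counted as more severe or as related.

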14.6 MISSING CAUSAL RELATIONSHIP TO STUDY TREATMENT FOR ADVERSE EVENTS

[If the 3-point scale for relationship to study treatment is used (ie, “Not related,” “Possibly related,” and “Related”), the relevant text below may need to be modified accordingly. For example, “causal relationship” would become “relationship” and “yes” would become “*related*.”]

If the causal relationship to the study treatment is missing for an AE that started on or after the date of the first dose of study treatment, a causality of yes will be assigned. The imputed values for causal relationship to study treatment will be used for the incidence summary; the values will be shown as missing in the data listings.

14.7 MISSING DATE INFORMATION FOR ADVERSE EVENTS

The following imputation rules only apply to cases in which the start date for AEs is incomplete (ie, partly missing).

Missing month and day

- If the year of the incomplete start date is the same as the year of the first dose of study treatment, the month and day of the first dose of study treatment will be assigned to the missing fields
- If the year of the incomplete start date is before the year of the first dose of study treatment, *December 31* will be assigned to the missing fields
- If the year of the incomplete start date is after the year of the first dose of study treatment, *January 1* will be assigned to the missing fields

Missing month only

- If only the month is missing, the day will be treated as missing and both the month and the day will be replaced according to the above procedure

Missing day only

- If the month and year of the incomplete start date are the same as the month and year of the first dose of study treatment, the day of the first dose of study treatment will be assigned to the missing day
- If either the year of the incomplete start date is before the year of the date of the first dose of study treatment or if both years are the same but the month of the incomplete start date is before the month of the date of the first dose of study treatment, the last day of the month will be assigned to the missing day
- If either the year of the incomplete start date is after the year of the date of the first dose of study treatment or if both years are the same but the month of the incomplete start date is after the month of the date of the first dose of study treatment, the first day of the month will be assigned to the missing day

If the stop date is complete and the imputed start date as above is after the stop date, the start date will be imputed by the stop date.

If the start date is completely missing and the stop date is complete, the following algorithm will be used to impute the start date:

- If the stop date is after the date of the first dose of study treatment, the date of the first dose of study treatment will be assigned to the missing start date
- If the stop date is before the date of the first dose of study treatment, the stop date will be assigned to the missing start date.

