8.3 Participant Training, Dispensing and Home Use of TrueTear

At Visit 2 (Day 0), participants randomized to the TrueTear application group will be provided a TrueTear device and disposable tips to take home with them and use daily. Participants will be instructed to use the device as described in the Patient Guide. They will receive training to perform intranasal neurostimulation and will receive a copy of the Patient Guide.

For the device application, participants will be told to turn on the unit by holding down the + button for approximately two seconds. There are five stimulation intensity levels and participants may adjust the level by pressing the + or – buttons to obtain a gentle tingling sensation. They will be instructed to fully insert the tips of the TrueTear into both nostrils simultaneously towards the top and front of the nose (as in Figure 2). Participants will be told they can cease stimulation by holding down the – button for approximately two seconds on the base unit or by withdrawing the tips from the nostrils. Participants will be instructed to replace the Tips with a new one if they do not feel any sensation.

For the initial in-office device application at Visit 2 (Day 0), each participant will be told that the application will take place for approximately eight minutes and that the entire procedure will occur while the participant is seated and positioned in a slit lamp to allow for simultaneous viewing of meibomian gland activity in the lower lid and for collection of lid and tear film temperature data.

At Visit 3 (Day 7), prior to in-office application and evaluation of tear secretion, trained clinical personnel will review procedures for the proper use of the device (e.g., correct positioning intranasally, frequency and duration of use, daily replacement and disposal of tips, etc.) with participants. As the device internally records the frequency and duration of device use, study staff may review this information with participants. Participants will be told that the in-office application of TrueTear at this visit should last for approximately three minutes.

Figure 2 Use of TrueTear

(L) Starting position and (R) Correct application position by inserting the disposable tips fully into the nasal cavity and to the front of the nose.

Note: Sponsor representatives may be present at visits to assist in training participants on the use of the device.

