14.8.1 Incomplete Start Date

The following rules will be applied to impute the missing numeric fields for an incomplete prior or concomitant medication start date. If the stop date is complete (or imputed) and the imputed start date is after the stop date, the start date will be imputed using the stop date.

Missing month and day

- If the year of the incomplete start date is the same as the year of the first dose of study treatment, the month and day of the first dose of study treatment will be assigned to the missing fields
- If the year of the incomplete start date is before the year of the first dose of study treatment, *December 31* will be assigned to the missing fields
- If the year of the incomplete start date is after the year of the first dose of study treatment, *January 1* will be assigned to the missing fields

Missing month only

- If only the month is missing, the day will be treated as missing and both the month and the day will be replaced according to the above procedure

Missing day only

- If the month and year of the incomplete start date are the same as the month and year of the first dose of study treatment, the day of the first dose of study treatment will be assigned to the missing day
- If either the year of the incomplete start date is before the year of the date of the first dose of study treatment or if both years are the same, but the month of the incomplete start date is before the month of the date of the first dose of study treatment, the last day of the month will be assigned to the missing day.
- If either the year of the incomplete start date is after the year of the date of the first dose of study treatment or if both years are the same, but the month of the incomplete start date is after the month of the date of the first dose of study treatment, the first day of the month will be assigned to the missing day

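### SAP 14.7 dates some AEs to Day 0 although a partial stop date shows they ended before treatment, and gives no start date to undated AEs that stopped on Day 0, are ongoing or have a partial stop date

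*SAP*

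**What the plan says.** SAP 14.7 handles AE start dates in three steps.

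- **Scope.** The section opens: "The following imputation rules only apply to cases in which the start date for AEs is incomplete (ie, partly missing".
- **Partly missing start.** If month and day are missing and the year is that of first dose, the start becomes the first-dose date. A start that lacks only the month is treated the same way, and its known day is ignored. A cap follows: "If the stop date is complete and the imputed start date as above is after the stop date, the start date will be imputed" from the stop date.
- **Completely missing start.** "If the start date is completely missing and the stop date is complete, the following algorithm will be used to impute the start date". There are two branches. The first: "If the stop date is after the date of the first dose of study treatment, the date of the first dose of study treatment" is assigned. The second: "If the stop date is before the date of the first dose of study treatment, the stop date will be assigned".

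Nothing in 14.7 imputes an AE stop date.

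Two other rules use the resulting start date. SAP 14.5 fills a blank severity as mild for an AE that began before Day 0 and as severe for one that began on Day 0 or later. SAP 14.6 covers a blank causal relationship: "missing for an AE that started on or after the date of the first dose of study treatment, a causality of yes will be assigned".

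SAP 10.1 tabulates treatment-emergent AEs (TEAEs) and treatment-related TEAEs by arm. It defines a TEAE by the event being present at or after first application, or worsening after it. Protocol 9.0 starts AE capture at study entry, so AEs from before treatment are collected.

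**The concern.** The cap exists to stop an imputed start from landing after the AE had ended, but it looks only at complete stop dates. A stop recorded as month and year can be just as conclusive: if that month is earlier than the month of Day 0, the AE ended before treatment. The rule still moves its start to Day 0.

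For completely missing starts, the two strict branches leave out equality, whereas 14.5 and 14.6 both put the first-dose date on the treatment side. An unresolved AE has no stop date, so it falls outside the algorithm altogether. So does an AE with a partial stop date.

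Comparing safety is part of the primary objective (Protocol 2.0, SAP 4.0), and the by-arm AE tables carry that comparison. Where the text gives no date or an impossible one, a programmer has to improvise in an open-label study with the events already known.

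**Working it through.** The plan states no figure on this point, so there is none to reproduce. The check applies the rules of 14.7 literally.

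**Inputs.** Day 0 = 6 September 2017 (assumed, for illustration). Time before treatment: about 44 − 30 = 14 days (Protocol 8.10 and 4.0). Arm size: 70 / 2 = 35 enrolled, or 60 / 2 = 30 completing (Protocol 5.1).

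**Single cases**

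| Start recorded | Stop recorded | Start assigned by 14.7 |
|---|---|---|
| 2017 | 31 Aug 2017 | 31 Aug 2017 (cap works) |
| 2017 | Aug 2017 | 6 Sep 2017 = Day 0, after the known end |
| missing | 5 Sep 2017 | 5 Sep 2017 |
| missing | 7 Sep 2017 | 6 Sep 2017 = Day 0 |
| missing | 6 Sep 2017 | none: neither branch is met |
| missing | ongoing | none: stop not complete |
| missing | Sep 2017 | none: stop not complete |

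**How general the first fault is.** Take every Day 0 from 1 July 2017 to 30 June 2018 (assumed; 365 dates) and every AE that starts and stops within the 14 days before it. That is 14 × 15 / 2 = 105 start and stop pairs per Day 0, or 365 × 105 = 38,325 in all.

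- *Stop date complete:* none of the 38,325 is dated to Day 0 or later, whichever part of the start is missing.
- *Stop day missing, stop month before the Day 0 month:* if Day 0 is the j-th of its month, the stop must be at least j days earlier, which leaves (15 − j)(16 − j) / 2 pairs. Summed over j = 1 to 14 this is 14 × 15 × 16 / 6 = 560 per month boundary, and 12 × 560 = 6,720 in all.
- At the year-end boundary the recorded start year is earlier than that of Day 0, so the start becomes 31 December and is correctly before treatment: 560 pairs.
- The other 11 × 560 = 6,160 of 6,720 are dated to Day 0. This holds both for a start with month and day missing and for one with only the month missing, so 2 × 6,160 = 12,320 patterns in all.

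These are counts of possible date patterns. They say when the rule fails, not how often such records occur.

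**What the second fault switches off.** With no start date, neither branch of 14.5 is met, so a blank severity stays blank. The condition in 14.6 cannot be shown to hold, so a blank causality is not set to yes.

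**Size of one misclassified participant.** 1 / 35 = 2.86 percentage points of an arm as enrolled; 1 / 30 = 3.33 of an arm of completers.

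**The case against.** **TEAE status does not need a start date.** A reader might infer that an undated ongoing AE drops out of the TEAE table. The documents do not support that: 10.1 asks whether the event was present, and an ongoing AE was. An AE that stopped on Day 0 may qualify too, although the dates alone do not show whether it was still present at the application. This part stands. The firm loss in the second fault is limited to the 14.5 and 14.6 defaults, and only where severity or causality is blank as well. The first fault is not rescued in the same way. An AE with its start set to Day 0 meets the definition on its assigned date, and the SAP does not tell the programmer to prefer the partial stop month.

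**Related counts.** A reader might infer that device-related counts go wrong in both directions as a matter of course. Each direction needs a blank causality field. Protocol 9.3 offers a *not applicable* category for participants not yet exposed. If that or *not related* was recorded, the first fault inflates only the all-TEAE count.

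**Day 0 events.** A reader might infer that the gap hides reactions to the first in-office TrueTear session, for which participants are told the "application will take place for approximately eight minutes". Those events occur at the slit lamp in front of staff, so a wholly blank start date beside a complete stop date is unlikely there. Protocol 13.6 also makes the investigator responsible for complete records. This stands as a reason to expect few cases.

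**The medication rule.** SAP 14.8.1 has a cap worded "If the stop date is complete (or imputed) and the imputed start date is after the stop date", and a reader might infer that the SAP already protects medications against this error. It does not. When both dates are incomplete, 14.8 imputes the start first, so no imputed stop exists yet. 14.8.2 then moves an imputed stop that precedes the start up to the start. With the same dates and a last dose about 30 days after Day 0, start 2017 and stop August 2017 give a start of 6 September, a stop of 31 August, and then a stop reset to 6 September.

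**Visibility.** The AE summaries are counts and percentages with no stated test, and every AE is listed, so an undated event can still be seen. This also stands.

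**Conclusion.** Both faults hold on a literal reading, and the point is minor. The first is more than missing detail: a stated rule assigns a date that the record itself disproves. It needs a start with the month missing in the year of first dose, and a partial stop date in a month of that year before the month of Day 0. The second is a gap in coverage that departs from the first-dose convention in 14.5 and 14.6.

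The number of affected records cannot be derived from the documents. It is probably small, which is a judgement. One participant moves an arm of 35 by about 2.9 percentage points. The effect on the TEAE and related counts is therefore possible rather than certain, and for severity and relatedness it depends on those fields being blank.

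**What to change.** Amend 14.7 in three places.

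- **(a) Cap.** If the imputed start falls after the latest date compatible with the stop date, complete or partial, use that latest date.
- **(b) Completely missing start.** Remove the precondition of a complete stop date. Assign the first-dose date if the stop is on Day 0 or later, if the AE is ongoing or the stop is missing, or if the stop is partial and not clearly before Day 0. Otherwise assign the stop date, or the latest date compatible with a partial one.
- **(c) Opening sentence.** Reword it to cover completely missing start dates. Read strictly, it now excludes the algorithm given later in the same section.

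In the examples above, start 2017 with stop August 2017 becomes 31 August. The undated AEs with stop 6 September, stop September 2017 or no stop become 6 September. All 12,320 mis-dated patterns move to before Day 0.

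The cost is a few lines of text and a small programming change, with no new data. The downside is that a few undated events may be counted as treatment-emergent, severe or related that otherwise would not be. That is the conservative direction the SAP already takes in 14.5 and 14.6. The SAP is at revision 2 and the documents give no database lock date. If the AE tables already exist, list the affected records and rerun those tables.
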